10.6 Quality Assurance Audit

A Sponsor representative or designee may request access to all study records, including source documentation, for inspection during a Quality Assurance audit.

If an investigator is contacted by a Regulatory Agency in relation to this study, the Investigator will notify Sponsor immediately. The Investigator and Research Coordinator must be available to respond to reasonable requests and audit queries made during the audit process. The Investigator must provide the Sponsor with copies of all correspondence that may affect the review of the current study (e.g., Form Food and Drug Administration (FDA) 483, Inspectional Observations, Warning Letters, Inspection Reports, etc.). The Sponsor may provide any needed assistance in responding to regulatory audits.

10.7 Clinical Events Committee (CEC)

The Clinical Events Committee (CEC) is an independent adjudication body comprised of qualified physicians who are not participants in the clinical investigation. The CEC will review and adjudicate pre-specified events reported by investigators or identified by Safety personnel for the clinical investigation as defined in the CEC charter and according to definitions provided in this CIP.

11 DATA HANDLING AND RECORD KEEPING

Sponsor and/or its affiliates will maintain documentation of the systems and procedures used in data collection for the duration of the study.

CRF data collection will be performed through a secure web portal and only authorized personnel will access the EDC system using a unique username and password to enter, review or correct data. Passwords and electronic signatures will be strictly confidential.

The data will be subjected to consistency and validation checks within the EDC system and supplemental review by the Sponsor.

At the end of the study, completed CRF images with the date-and-time stamped electronic audit trail indicating the user, the data entered, and any reason for change (if applicable) will be provided to the investigational sites, if requested.

For the duration of the study, the Investigator will maintain complete and accurate documentation including, but not limited to, medical records, study progress records, laboratory reports, CRFs, signed ICFs, correspondence with the IRB/EC, and study monitor/Sponsor, adverse event reports, and information regarding subject discontinuation or completion of the study.

11.1 Protection of Personally Identifiable Information

The Sponsor respects and protects personally identifiable information collected or maintained for this study.

The Sponsor implements technical and physical access controls to ensure that Personal Information is accessible only to and processed only on a 'need to know' basis, including periodic review of access rights, and revocation of access when an individual's employment is terminated or the individual transitions to a role that does not require access to Personal Information, and appropriate restrictions on physical access to premises, facilities, equipment, and records containing Personal Information.

The Sponsor requires the investigational sites to enter only pseudonymous Personal Information (key-coded) necessary to conduct the study, such as the patient's medical condition, treatment, dates of treatment, etc., into Sponsor's data management systems. The Sponsor discloses as part of the study informed consent process that some Sponsor representatives still may see Personal Information at the participating sites for technical support of the participating physicians on the device implant or procedures, monitoring and quality control purposes. All parties will observe confidentiality of Personal Information always throughout the study. All reports and data publications will preserve the privacy of each subject and confidentiality of his/her information.

The Sponsor data management systems and processes were designed, developed, and tested according to industry standards to appropriately safeguard Confidential Information (including any Personal Information) against unauthorized access and/or interference by third parties, intrusion, theft, destruction, loss or alteration. Study data are encrypted in transit and at rest.

The Sponsor maintains a Privacy Incident procedure that complies in all respects with Applicable Law and industry best practices.

11.2 Data Management Plan

A Data Management Plan (DMP) will describe procedures used for data review, data cleaning, and issuing and resolving data discrepancies. If appropriate, the Sponsor may update the DMP throughout the duration of the study. The Sponsor will track and document control all revisions.

11.3 Source Documentation

Regulations and GCP require the Investigator to maintain information in the subject's original medical records that corroborates data collected on the CRFs. To comply with these regulatory requirements/GCP, sites should include the following information in the subject record at a minimum and if applicable to the study:

- Medical history/physical condition of the subject before involvement in the study sufficient to verify CIP entry criteria
- Dated and signed notes on the day of entry into the study referencing the Sponsor, CIP number, subject ID number, and a statement that informed consent was obtained
- Dated and signed notes from each subject visit (for specific results of procedures and exams)

- AEs reported and their resolution, including supporting documents, such as discharge summaries, catheterization laboratory reports, ECGs, and lab results including documentation of site awareness of SAEs and of investigator assessment of device relationship for SAEs.
- CIP-required laboratory reports, reviewed and annotated for clinical significance of out of range results (if applicable).
- Notes regarding CIP-required and prescription medications taken during the study (including start and stop dates)
- Subject's condition upon completion of or withdrawal from the study
- Any other data required to substantiate data entered into the CRF
- Patient reported outcome measures may be completed using CRF worksheets. This serves as source documentation.

11.4 Case Report Form Completion

Site research personnel trained on the CIP and CRF completion will perform the primary data collection clearly and accurately based on source-documented hospital and/or clinic chart reviews. The investigator will ensure accuracy, completeness, legibility, and timeliness of the data reported to the Sponsor on the CRFs and in all required reports.

Sites will collect data on all subjects registered into the study. Only authorized site personnel will be permitted to enter the CRF data through the EDC system deployed by the Sponsor. The Sponsor will use an electronic audit trail to track any subsequent changes of the entered data.

11.5 Record Retention

The Sponsor and Investigator/Site will archive and retain all documents pertaining to the study as per the applicable regulatory record retention requirements. The Investigator must obtain permission from Sponsor in writing before destroying or transferring control of any study records.

12 ETHICAL CONSIDERATION

12.1 Institutional Review Board/Medical Ethics Committee Review and Approval

The Principal Investigator at each investigational site will obtain IRB/EC approval for the CIP and ICF/other written information provided to the patient prior to consenting and enrolling patients in this study. The site must receive the approval letter prior to the start of this study and provide a copy to the Sponsor.

Sites will submit any amendments to the CIP as well as associated ICF changes to the IRB/EC and written approval obtained prior to implementation, according to each institution's IRB/EC requirements.

No changes will be made to the CIP or ICF or other written information provided to the patient without appropriate approvals, including IRB/EC, the Sponsor, and the regulatory agencies (if applicable).

Until the study is completed, the Investigator will advise his/her IRB/EC of the progress of this study, per IRB/EC requirements. Written approval must be obtained from the IRB/EC yearly to continue the study, or according to each institution's IRB/EC requirements.

Sites will not perform any investigative procedures, other than those defined in this CIP, on the enrolled subjects without the written agreement of the IRB/EC and the Sponsor.

13 CLINICAL INVESTIGATION CONCLUSION

The study will be concluded when:

- All sites are closed AND
- The final report has been provided to investigators or the Sponsor has provided formal documentation of study closure.

In addition, the Sponsor will submit the study report within one year of the end of the study to the investigational sites, competent authorities, and reviewing IRBs and ECs.

14 PUBLICATION POLICY

The data and results from the study are the sole property of the Sponsor. The Sponsor shall have the right to access and use all data and results generated during the study. The Investigators will not use this study-related data without the written consent of the Sponsor for any purpose other than for study completion or for generation of publication materials, as referenced in the Clinical Trial Agreement. Single-center results are not allowed to be published or presented before the multi-center results. The Sponsor must review and approve any proposals for publications or presentations by the investigators in a timely manner in compliance with the Sponsor's publication policy set forth in the Clinical Trial Agreement.

The Sponsor will be responsible for determining whether to register the study on www.clinicaltrials.gov or any other clinical trials, in accordance with the International Committee of Medical Journal Editors guidelines, or any other applicable guidelines. In the event the Sponsor determines that the study should be registered, the Sponsor shall be responsible for any such registration and results posting as required by the ClinicalTrials.gov website. Institution and/or Principal Investigator(s) shall not take any action to register the study.

15 RISK ANALYSIS

15.1 Anticipated Clinical Benefits

JETi is similar in development and design to other mechanical thrombectomy devices that aspirate and remove thrombus in the peripheral vasculature. The JETi System functions by delivering a stream of high-pressure saline through a catheter to aspirate the thrombus and remove the material from the vessel. Use of the JETi System for mechanical thrombectomy may allow for thrombus removal without the use of thrombolytic drugs with an acceptable device-related serious adverse event rate.

15.2 Foreseeable Adverse Events and Anticipated Adverse Device Effects

Risks associated with the JETi Thrombectomy System and the procedure, together with their likely incidence, are described in the instructions for use (IFU) and **Appendix V**. There may be risks related to the device under investigation that are unknown at present. Likewise, the exact frequency of the risk may be unknown.

15.3 Residual Risks Associated with the Device Under Investigation, as Identified in the Risk Management Report / Risk Analysis Report

Risk analysis of the JETi System has been performed in accordance with the Risk Management File (including Risk Management Plan, Failure Mode Effect Analysis (FMEA), and Hazard Analysis (HA)) [REDACTED] to systematically identify potential hazards associated with the design and use of this device. Based upon bench testing and prior clinical study data, all risks have been identified and mitigated as far as possible through application of appropriate controls and inspections and determined to be within acceptable levels.

Residual risks are likewise disclosed in the IFU in the form of clear instructions of what actions to take or to avoid, to avoid a hazardous situation of harm from occurring (contra-indications, warnings, and precautions). The anticipated AEs disclosed in the IFU [REDACTED] provide further information to enable the user, and potentially the patient, to make an informed decision that weighs the residual risk against the benefit of using the device.

15.4 Risks Associated with Participation in this Clinical Investigation

There are no additional risks related to the participation in this clinical investigation: risks related to the procedure have been included in the product IFU, all study procedures are considered standard of care.

15.5 Steps Taken to Control or Mitigate Risks

In-depth recommendations, special precautions and instructions for use related to the device and device performance are included in the IFU. Patient selection, [REDACTED] evaluated in this trial are included within this document (**Section 5.3 Eligibility Criteria**); [REDACTED]

The sponsor conducted a comprehensive risk analysis for the device and per ISO 14971 - "Medical devices – Application of risk management to medical devices". In order to ensure the highest probability of safety for the device design, the sponsor implemented design features, preventive steps, or completed pre-clinical evaluations to address and reduce the risks identified wherever possible.

The JETi System is made of materials known to be safe for human use and the device is already cleared for removal of intravascular thrombus.

The risk to the subjects is mitigated by selection of investigators with proficient knowledge and experience in the removal of intravascular thrombus. Investigators will receive comprehensive training by the sponsor on device handling prior to use during this study.

Investigator Selection and Training: It is also stated in the IFU that the devices can only be used by physicians who have received appropriate training on how to use the device. This statement is interpreted to mean that the physician users are expected to be aware of the known and foreseeable safety risks associated with the use of the devices including the surgical and/or non-surgical treatment of these conditions.

Ensuring strict adherence to the clinical investigation protocol: The clinical investigation will be carefully monitored by the Sponsor monitor (or designee) to ensure adherence to the CIP. Adverse events and device deficiencies will be reported to Abbott/designee and will be monitored internally for safety surveillance purposes.

15.6 Risk to Benefit Rationale

A thorough risk assessment was completed, applicable control measures were applied, and analysis confirmed that there are no unacceptable residual risks. Based on the risk management review and with management approval of the residual risks, the device design, device usability, and manufacturing process of the JETi Peripheral Catheter has an acceptable level of risk for its intended use.

The JETi system is an FDA-cleared device and a part of the current standard of care for clot removal in the peripheral vasculature. [REDACTED]

[REDACTED] Use of the JETi System for mechanical thrombectomy may allow for thrombus removal without the use of thrombolytic drugs with an acceptable device-related serious adverse event rate. Taking these into consideration, the clinical benefits that may be expected from the removal of emboli and thrombus from the peripheral vasculature with the JETi System outweigh the possible risks that patients may experience when participating in this clinical investigation.

APPENDIX I: ABBREVIATIONS AND ACRONYMS

Acronym or Abbreviation	Complete Phrase or Definition
AE	Adverse Event
ABI	Ankle Brachial Index
BUN	Blood Urea Nitrogen
CDT	Catheter-Directed Thrombolysis
CFR	Code of Federal Regulations
CIP	Clinical Investigation Plan
CRF	Case Report Form
EC	Ethics Committee
EU	European Union
eGFR	Estimated Glomerular Filtration Rate
EDC	Electronic Data Capture
FDA	Food and Drug Administration
GCP	Good Clinical Practice
HIPAA	Health Insurance Portability and Accountability Act Intersocietal Commission for the Accreditation of Vascular
ICF	Informed Consent Form
IFU	Information for Use
INR	International Normalized Ratio
IRB	Institutional Review Board
IVC	Inferior Vena Cava
JETi	JET Enhanced Thrombectomy intervention
LMWH	Low Molecular Weight Heparin
PT	Prothrombin Time
PTS	Post Thrombotic Syndrome
aPTT	Activated Partial Thromboplastin Time
QOL	Quality of Life
SAE	Serious Adverse Event
SDU	Saline Drive Unit
SF-12	Short Form-12

APPENDIX II: DEFINITIONS

Amputation

The removal of a body extremity by surgery. For this study, the definition of amputation will only apply to amputations of the limb that was treated.

Minor amputation: amputation below the ankle

Major amputation: amputation above the ankle

Ankle Brachial Index (ABI)

The ABI is the ratio of the ankle to arm pressure, and it is calculated by dividing the higher systolic blood pressure of the two arteries (Dorsalis pedis or Posterior tibial) at the ankle of the assessed leg by the higher of the two brachial systolic blood pressures.

Calculation of the Ankle Brachial Index:

ABI = Highest Ankle Systolic Pressure/Highest Brachial Systolic Pressure

Death (per ARC 1)

When possible, death will be classified according to underlying cause. Death within 30 days of the study procedure will be classified as procedure related unless medical history or autopsy findings demonstrate otherwise.

Cardiac death:

Any death due to proximate cardiac cause (e.g., MI, low-output failure, fatal arrhythmia), unwitnessed death, or death of unknown cause.

Vascular death:

Death caused by noncoronary vascular causes, such as cerebrovascular disease, pulmonary embolism, ruptured aortic aneurysm, dissecting aneurysm, or other vascular diseases.

Non-cardiovascular death:

Any death not covered by the above definitions, such as death caused by infection, malignancy, sepsis, pulmonary causes, accident, suicide, or trauma.

Dissection

National Heart, Lung, and Blood Institute (NHLBI) Dissection Classification System:

- A. Minor radiolucencies within the lumen during contrast injection with no persistence after dye clearance.
- B. Parallel tracts or double lumen separated by a radiolucent area during contrast injection with no persistence after dye clearance.
- C. Extraluminal cap with persistence of contrast after dye clearance from the lumen.
- D. Spiral luminal filling defects.
- E. New persistent filling defects.
- F. Non-A-E types that lead to impaired flow or total occlusion.

Note: Type E and F dissections may represent thrombus.

Lower Extremity Deep Vein Thrombosis or Deep Venous Thrombosis (DVT)

DVT occurs when a blood clot forms in a deep vein, usually in the lower leg, thigh, or pelvis, but it can also occur in the arm.

For this study, the definition of Lower Extremity Deep Vein Thrombosis will apply to lower extremity venous thrombosis involving the femoral, common femoral, or iliac veins, or popliteal, or inferior vena cava (IVC) alone or in combination.

Acute clot for this study is defined based on signs and symptoms of onset of <2 weeks

Subacute clot for this study is defined based on signs and symptoms of onset of 2-6 weeks

Chronic clot for this study is defined based on signs and symptoms of onset of >6 weeks.

Major Bleeding (per BARC)

- BARC 3a: Overt bleeding plus hemoglobin drop of 3 to < 5 g/dL (provided hemoglobin drop is related to bleed); transfusion with overt bleeding or
- BARC 3b: Overt bleeding plus hemoglobin drop \geq 5 g/dL (provided hemoglobin drop is related to bleed); cardiac tamponade; bleeding requiring surgical intervention for control; bleeding requiring IV vasoactive agents or
- BARC 5a Probable fatal bleeding; no autopsy or imaging confirmation but clinically suspicious or
- BARC 5b Definite fatal bleeding; overt bleeding or autopsy, or imaging confirmation

Pulmonary Embolism (per AHA)

Low-risk Pulmonary Embolism: Acute PE and the absence of the clinical markers of adverse prognosis that define massive or submassive PE

Massive Pulmonary Embolism: Acute PE with sustained hypotension (systolic blood pressure <90 mm Hg for at least 15 minutes or requiring inotropic support, not due to a cause other than PE, such as arrhythmia, hypovolemia, sepsis, or left ventricular [LV] dysfunction), pulselessness, or persistent profound bradycardia (heart rate <40 bpm with signs or symptoms of shock).

Sub-massive Pulmonary Embolism: Acute PE without systemic hypotension (systolic blood pressure \geq 90 mm Hg) but with either RV dysfunction or myocardial necrosis.

- RV dysfunction means the presence of at least 1 of the following:
 - RV dilation (apical 4-chamber RV diameter divided by LV diameter >0.9) or RV systolic dysfunction on echocardiography
 - RV dilation (4-chamber RV diameter divided by LV diameter >0.9) on CT
 - Elevation of BNP (>90 pg/mL)
 - Elevation of N-terminal pro-BNP (>500 pg/mL); or
 - Electrocardiographic changes (new complete or incomplete right bundle-branch block, anteroseptal ST elevation or depression, or anteroseptal T-wave inversion)
- Myocardial necrosis is defined as either of the following:
 - Elevation of troponin I (>0.4 ng/mL) or
 - Elevation of troponin T (>0.1 ng/mL)

Renal Failure

Acute renal failure, also known as acute kidney injury (AKI), definition as per Kidney Disease Improving Global Outcomes (KDIGO):

- Increase in serum creatinine of ≥ 0.3 mg/dL within 48 hours or $\geq 50\%$ within 7 days OR
- Urine output of <0.5 mL/kg/hour for >6 hours

Symptomatic Pulmonary Embolism

Define as per Society of Interventional Radiology (SIR) Quality Improvement Guidelines for the Treatment of Lower-Extremity Deep Vein Thrombosis with Use of Endovascular Thrombus Removal:

Episodes of DVT or PE can be symptomatic (the patient had symptoms and/or signs that prompted evaluation for DVT or PE) or asymptomatic (DVT or PE was detected on an imaging study in a patient without symptoms)

Recurrent Deep Venous Thrombosis (DVT)

Deep Vein Thrombosis that recurs in the treated limb.

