4.1 Primary Endpoints

4.1.1 Arterial and Arteriovenous Subjects

For subjects treated for arterial thrombosis (may include diagnoses such as acute limb ischemia, chronic limb ischemia/chronic limb threatening ischemia, peripheral artery disease, etc.) or arteriovenous (AV graft, AV fistula) thrombosis, all endpoints are descriptive.

For subjects treated for arterial or arteriovenous thrombosis, the primary endpoints are:

- **Clot removal grade** for each JETi-treated target vessel from pre-JETi angiogram to post-JETi angiogram (post-JETi thrombectomy and prior to any adjunctive therapies to treat underlying culprit lesions) per the grades in **Table 1** (vessel basis). The independent imaging core laboratory will be responsible for assessing this endpoint.
- **Composite of JETi-related major adverse events** (MAEs) up to 30 days post-JETi procedure, defined as the following JETi-related events adjudicated by a clinical events committee (CEC) (subject basis) death, major amputation of the treated limb, or major bleeding. Refer to **Appendix II** for definitions of major adverse events.

Table 1. Clot Removal Grade

Grade I	< 50% reduction
Grade II	50- <95% reduction
Grade III	95 - 100% reduction

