4.1.2 Venous Subjects

For this study, lower extremity deep vein thrombosis or deep venous thrombosis is defined as lower extremity venous thrombosis involving the femoral, common femoral, iliac, popliteal, or inferior vena cava (IVC) alone or in combination.

For subjects treated for lower extremity DVT, the primary endpoints are:

- **Percent of treated vessel(s) with $\geq 75\%$ venous thrombus reduction** from pre-JETi venogram to final venogram (post-JETi AND after any/all adjunctive therapies to treat underlying culprit lesions) via modified Marder score (limb basis). The independent imaging core laboratory will be responsible for assessing this endpoint.
If no adjunctive therapies or devices are used after JETi, post-JETi modified Marder score is also final score.
- **Composite of JETi-related major adverse events (MAEs)** up to 30 days post-JETi procedure, defined as the following JETi-related events adjudicated by a clinical events committee (CEC): death, symptomatic pulmonary embolism (PE), major bleeding, or re-thrombosis of JETi-treated vessel(s). Refer to **Appendix II** for definitions of major adverse events.

The effectiveness outcome for subjects treated for venous thrombosis that is not lower extremity DVT as defined in Appendix II (e.g., upper extremity DVT) will be assessed by clot removal grade, as defined in Section 4.1.1.

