6 TREATMENT AND EVALUATION OF ENDPOINTS

For this study, the following definitions apply:

- **Index procedure:** the entire intervention to treat the subject's peripheral vascular thrombosis. A subject's procedure may include more than one session if the subject is removed from the interventional suite and placed in a holding area with the intention of returning to the suite for additional treatments either the same day or following day (e.g., catheter placement or removal for CDT).
- **Treatment:** the individual techniques performed during a procedure to address the subject's peripheral vascular thrombosis (e.g., JETi thrombectomy, balloon angioplasty, stent placement, or catheter-directed thrombolysis (CDT)). Note that "JETi treatment" will refer to treatment during which the JETi Thrombectomy system is used.

NOTE: A subject's treatment is determined by the treating physician based on the clinical situation and institutional practices.

- **Session:** a session is the in and out period within an interventional suite that a subject is receiving treatment. A subject's procedure may include more than one session if the subject is removed from the interventional suite and placed in a holding area with the intention of returning to the suite for additional treatments either the same day or following day (e.g., catheter placement or removal for CDT).

NOTE: Treatment for unexpected re-thrombosis is an adverse event and should not be considered as an additional session of the initial procedure. Refer to **Section 7.1.1**.

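### Apart from cardiac tamponade, the major bleeding definition has no criterion based on site, so some JETi-related non-fatal intracranial bleeds would fall outside the primary safety composite

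*Combined protocol and SAP*

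**What the plan says.** Appendix II of the combined protocol and SAP defines major bleeding, with a reference to BARC, as four categories joined by the word or:

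- "BARC 3a: Overt bleeding plus hemoglobin drop of 3 to < 5 g/dL (provided hemoglobin drop is related to bleed); transfusion with overt bleeding or"
- 3b, which covers a hemoglobin drop of 5 g/dL or more and tamponade of the heart, and then lists "bleeding requiring surgical intervention for control; bleeding requiring IV vasoactive agents or"
- the two fatal categories, 5a when a fatal bleed is suspected on clinical grounds only, and 5b when it is definite

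Both primary safety composites include this term. For arterial and arteriovenous subjects (Section 4.1.1) the JETi-related components are "death, major amputation of the treated limb, or major bleeding. Refer to" the definitions appendix. For lower extremity DVT (Section 4.1.2) they are "death, symptomatic pulmonary embolism (PE), major bleeding, or re-thrombosis of JETi-treated vessel(s). Refer to" the same appendix. Section 8.2.1 repeats both composites. Section 10.7 has the CEC adjudicate under its charter and the plan's own definitions. Sections 4.2.2 and 4.2.3 make procedural success depend on there being no JETi-related MAE within 5 days of registration or by discharge, whichever is first.

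**The concern.** Intracranial bleeding is serious because of where it occurs, not because of how much blood is lost. A definition built on hemoglobin loss, transfusion and intervention can miss it. The question is relevant to this study because Section 6 counts "or catheter-directed thrombolysis (CDT") among the treatments that a procedure may include, and Section 6 also has thrombolytics used in the index procedure recorded.

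At stake is the face validity of the primary safety result. A subject could have a disabling, device-related bleed in the head and still be tabulated as free of MAEs. If the vessel was opened and the bleed was early, the same subject could be reported as a procedural success.

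**Working it through.** The plan gives no event rate, power or target for MAEs, so there is no figure of its own to reproduce. The check is mainly a reading of the text, with a short calculation for scale.

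**Step 1: test the event against each listed criterion.** Take a non-fatal intracranial bleed judged JETi-related, with a hemoglobin drop below 3 g/dL and no transfusion, surgical control or IV vasoactive agents.

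| Criterion (Appendix II) | Met? |
|---|---|
| 3a: overt bleeding, hemoglobin drop 3 to <5 g/dL | No, drop is below 3 |
| 3a: transfusion with overt bleeding | No |
| 3b: overt bleeding, hemoglobin drop of at least 5 g/dL | No |
| 3b: cardiac tamponade | No, different site |
| 3b: surgical control | No |
| 3b: IV vasoactive agents | No |
| 5a, 5b: fatal bleeding | No, non-fatal |

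No criterion is met. The list runs on without a redaction mark, so blacked-out text does not explain the result.

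**Step 2: look for another MAE component that would catch it.** The remaining arterial and arteriovenous components are death and major amputation. The remaining venous components are death, symptomatic pulmonary embolism and re-thrombosis. None applies, and neither composite has a stroke or intracranial hemorrhage component.

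**Step 3: follow the definition downstream.** The MAE-component endpoints and procedural success (Sections 4.2.2 and 4.2.3) rest on the same MAE terms, so the omission carries into them.

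**Step 4: see where the event is still recorded.** Section 7.3.1 requires all SAEs and all device- and procedure-related adverse events to be reported through the 30-day visit. A disabling bleed would probably meet the permanent-impairment or hospitalization criteria in Section 7.1.2. Section 4.2.1 makes CEC-adjudicated JETi-related adverse events a descriptive endpoint for all subjects.

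**Step 5: scale.** Section 8.3 plans about 20 subjects. The plan fixes no denominator for an overall MAE rate, so two are assumed: all 20 subjects together, and a vascular-bed group of 10. With x events in n subjects, the exact 95% limits are the 0.025 quantile of Beta(x, n − x + 1) and the 0.975 quantile of Beta(x + 1, n − x). For x = 0 the lower limit is 0 and the upper limit is 1 − 0.025^(1/n).

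| Assumed n | Bleed not counted | Bleed counted | Change |
|---|---|---|---|
| 20 | 0/20 = 0% (0 to 16.8%) | 1/20 = 5% (0.1 to 24.9%) | 5 points |
| 10 | 0/10 = 0% (0 to 30.8%) | 1/10 = 10% (0.3 to 44.5%) | 10 points |

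**The case against.** Several points can fairly be made on the other side.

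- **The affected set is narrow.** Only JETi-related events enter the composites. Section 7.2 has the investigator weigh evidence of another cause, and a head bleed during lysis has an obvious one. This stands: the gap concerns only bleeds that the CEC still judges JETi-related, and bleeds attributed to lysis alone would stay outside after any change.
- **The event is not lost.** This stands, as Step 4 shows. A reader might infer that a serious bleed would go unreported; the documents do not support that.
- **Nothing turns on the MAE rate.** Section 4 makes all endpoints descriptive, with no hypothesis testing, and the visible text ties no study-level threshold or stopping rule to the rate. This stands and keeps the point minor. Procedural success at subject level does depend on MAE status.
- **Adjudicators may have further guidance.** The CEC charter is not among the documents, and the reference to BARC might lead them to apply a category that is not printed. This is possible, but Section 10.7 also binds them to the plan's definitions, so the plan should settle the matter.

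Two stronger readings are tempting. A reader might infer that the list ignores bleeding site altogether; it does not, since tamponade is a site-specific item. A reader might also infer from the step between 3b and 5a that a category was dropped by mistake. The documents do not say what, if anything, lies between them or why these four were chosen, so the point rests on the printed criteria alone.

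**Conclusion.** The point holds as a narrow gap in a primary endpoint definition. By the printed text, a JETi-related, non-fatal intracranial bleed that meets none of the hemoglobin, transfusion, surgery or vasoactive criteria is not major bleeding, and so is not an MAE in either composite.

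The importance is low. The event is expected to be rare, but that is a judgement: no rate appears in the visible text, and the appendix on foreseeable event rates is blacked out. The 5-point and 10-point changes are illustrations that depend on the assumed denominators. The plan has two composites with different components and its pooling text is partly redacted, so a reader should not take 20 as the planned MAE denominator.

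**What to change.** Add to the major bleeding entry in Appendix II that non-fatal intracranial bleeding counts as major bleeding whatever the hemoglobin change. If other sites are meant to count, name each one, because a general phrase such as critical-site bleeding is undefined in the plan and would create a new adjudication question. If the sponsor prefers to leave such bleeds out, the plan should say so and give the reason. Align the CEC charter with whichever rule is adopted.

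The change adds no visit or test and does not alter the sample size. Its costs are a possibly marginally higher MAE rate and routine amendment handling, including the ethics committee steps in Sections 10.2 and 12.1.
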